5.2 Exclusion Criteria

Participants are excluded from the trial if any of the following criteria apply:

Diagnostic Assessments

- 1. Concurrent skin diseases on the hands (e.g. tinea manuum).
- 2. Active atopic dermatitis requiring medical treatment in regions other than the hands and feet.
- 3. Active psoriasis on any part of the body.
- 4. Hyperkeratotic hand eczema in combination with a history of psoriasis on any part of the body.
- 5. Clinically significant infection (e.g. impetiginised hand eczema) on the hands.

Medical Conditions

- 6. Participants who cannot receive alitretinoin for any of the following reasons:
 - a. Hepatic impairment, defined as alanine aminotransferase (ALT) and/or aspartate aminotransferase (AST) values >2×ULN, and/or prothrombin international normalised ratio (INR) >1.5×ULN.
 - b. Renal insufficiency, defined as creatinine clearance <60 mL/min calculated by use of the Cockcroft-Gault formula.
 - c. Uncontrolled hypercholesterolemia, defined as fasting cholesterol >1.5×ULN and/or fasting low-density lipoprotein (LDL) cholesterol >1.5×ULN.
 - d. Uncontrolled hypertriglyceridemia, defined as fasting triglyceridaemia 1.5×ULN.
 - e. Uncontrolled hypothyroidism, defined as thyroid-stimulating hormone >1×ULN and/or thyroxine <1×lower limits of normal.
 - f. Hypervitaminosis A, defined as retinol levels >1×ULN (e.g. due to the use of vitamin A supplements containing >2000 IU).
 - g. Known or suspected hypersensitivity either to alitretinoin, to other retinoids or to any of the excipients listed in the applicable alitretinoin label, in particular allergies to peanut or soya, or intolerance to sorbitol or fructose.
 - h. Any other contraindication to receive alitretinoin according to the investigator's judgement.

- 7. Clinically significant infection within 28 days prior to baseline which, in the opinion of the investigator, may compromise the safety of the participant in the trial, interfere with the evaluation of the IMP, or reduce the participant's ability to participate in the trial. Clinically significant infections are defined as:
 - a. A systemic infection.
 - b. A serious skin infection requiring parenteral (intravenous or intramuscular) antibiotics, antiviral, or antifungal medication.

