7.1 Discontinuation of Trial Treatment

It may be necessary for a participant to permanently discontinue the IMP. If the IMP is permanently discontinued, the participant will remain in the trial and attend an early termination visit, a follow-up visit 2 weeks after the last administration of IMP, the primary endpoint visit at Week 12 (for participants who discontinue the IMP prior to Week 12), and the nominal Week 24 visit. Female participants on alitretinoin treatment should have a pregnancy test performed 5 weeks after the last IMP administration. See the SoA (Table 1-1) for data to be collected at the time of IMP discontinuation and follow-up and for any further evaluations that need to be completed.

IMP must be discontinued permanently in case of the following:

- 1. An AE that, in the opinion of the investigator or sponsor's medical expert, contraindicates further dosing.
- 2. Evidence of pregnancy.
- 3. Intolerable CHE symptoms requiring the initiation of rescue medication (see Section 6.8.2).
- 4. Symptoms or AEs requiring treatment with prohibited medication or procedure (see Section 6.8.3).
- 5. Clinically important laboratory abnormalities in liver chemistry (see Appendix 6):
 - a. ALT and/or AST values >3×ULN with total bilirubin >2×ULN (unless elevated bilirubin is related to Gilbert Meulengracht Syndrome).
 - b. ALT and/or AST values >3×ULN with prothrombin INR >1.5×ULN.
 - c. Confirmed ALT and/or AST values >5×ULN (for more than 2 weeks).
- 6. For alitretinoin only, if participant develops depression, mood disturbance, psychosis, or aggression. Participant should be referred immediately to a mental health care professional for further assessment.
- 7. For alitretinoin only, if participant develops any symptoms requiring treatment discontinuation per local product information (e.g. signs of benign intracranial hypertension, increased lipids that cannot be controlled at an acceptable level, symptoms of pancreatitis, severe diarrhoea).

Trial treatments should be discontinued permanently in case of the following:

8. An IGA-CHE score of 4 (severe) after receiving 12 weeks of alitretinoin treatment or 16 weeks of delgocitinib treatment.

The primary reason for permanent discontinuation of IMP must be recorded in the medical records and on the end-of-treatment form in the eCRF where the following options are available:

- Adverse event.
- Death.
- Lost to follow-up.
- Pregnancy.
- Withdrawal by participant.
- Lack of efficacy.
- Other.

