9.3.11.3 Clinical Laboratory Evaluation

For laboratory parameters, the absolute values as well as the changes from baseline will be summarised by visit for each treatment group.

A shift table will be produced for relevant parameters showing the categories at baseline against those at each post-baseline visit.

For participants with post-baseline values, the number of events reported up to Week 26 will be summarised. For the following laboratory abnormalities endpoints, binary estimand strategy will be applied, as described in Section 9.3.6.3:

- Increased levels of triglycerides >3.42 mmol/L (fasted state).
- Increased levels of cholesterol >7.75 mmol/L (fasted state).
- Increased levels of ALT and/or AST >3×ULN (or >3×baseline if baseline was abnormal but <2×ULN).
- Increased levels of ALP > 2.5 × ULN.
- Increased levels of bilirubin >1.5×ULN up to Week 26.

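### The bilirubin and ALP exceedance endpoints have no baseline condition, so an eligible participant with an unchanged pre-existing elevation is counted as an on-trial event

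*Combined protocol and SAP*

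**What the plan says.** Table 3-2 (exploratory safety endpoints) and section 9.3.11.3 list five laboratory exceedance endpoints.

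- Bilirubin: "Increased levels of bilirubin >1.5×ULN up to Week 26".
- ALP: "Increased levels of ALP > 2.5 × ULN".
- ALT and/or AST above 3×ULN, with an alternative that uses baseline: "or >3×baseline if baseline was abnormal but <2×ULN".
- Fasting triglycerides above 3.42 mmol/L and fasting cholesterol above 7.75 mmol/L, with no reference to baseline.

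Section 9.3.11.3 applies the binary strategy of section 9.3.6.3 to all five; its summary measure is the difference in response rates with a 95% CI. Section 9.3.11.3 also plans absolute values and changes from baseline by visit, and shift tables for relevant parameters.

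On entry, exclusion criterion 6.a reads "Hepatic impairment, defined as alanine aminotransferase (ALT) and/or aspartate aminotransferase (AST) values >2×ULN" and adds a prothrombin INR limit. It names neither bilirubin nor ALP. The liver stopping rule in section 7.1, item 5a (repeated in section 10.6.2), carries an exception: "unless elevated bilirubin is related to Gilbert Meulengracht Syndrome".

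**The concern.** These endpoints are there to compare laboratory abnormalities that arise on treatment. For ALT/AST the plan guards against pre-existing elevation twice: eligibility removes values above 2×ULN, and the endpoint has a baseline clause. Bilirubin and ALP have neither guard. Since the authors wrote baseline into one definition, it cannot safely be read into the others. Adverse events have an explicit treatment-emergence rule (section 9.3.11.1); these laboratory endpoints do not.

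At stake are the absolute counts, any ratio taken from them, and how an imbalance between arms is read. A reader who sees more bilirubin exceedances in one arm could not tell from this endpoint whether they are new or were present on Day 1.

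**Working it through.** **1. The plan's own figure.** The documents state no rate, count or power for the laboratory endpoints. The only figure that can be checked is the primary sample size (section 9.5). With a difference of 7.5, SD 30, 1-sided 2.5% and 80% power: n per arm = 2 × (1.96 + 0.842)² × (30/7.5)² ≈ 251.2, so 252 per arm or 504 in total, against 510 planned. Power with 255 per arm is 80.6%. That figure reproduces and is not affected.

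**2. Can a participant enter above the cut-off?**

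| Parameter | Endpoint cut-off | Numeric entry limit | Baseline clause |
|---|---|---|---|
| ALT/AST | 3×ULN | 2×ULN (6.a) | yes |
| Bilirubin | 1.5×ULN | none | no |
| ALP | 2.5×ULN | none | no |
| Cholesterol | 7.75 mmol/L | 1.5×ULN (6.c) | no |
| Triglycerides | 3.42 mmol/L | 1.5×ULN (6.d, printed without an inequality sign, read here as above) | no |

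Exclusion criterion 13 reaches other abnormal laboratory findings only if they are clinically significant and either put the participant at risk or affect completion. So for bilirubin and ALP entry above the line is possible.

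**3. How often could one participant count?** Table 1-1 schedules chemistry after baseline at Weeks 4, 8, 12, 16, 20 and 24 and at follow-up: seven draws. Table 3-2 words the endpoint as a number of events, so seven per participant is the scheduled maximum.

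**4. Effect on the comparison (all rates assumed).** Let p be the share already above the cut-off who stay there, and take true new-onset incidences of 1% and 3% with 255 per arm. Observed rate = p + (1 − p) × incidence. The simple unstratified SE of the difference is √[(A(1 − A) + B(1 − B))/255], where A and B are the observed rates.

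| p | Counted without change, per arm | A | B | Risk ratio | Risk difference (points) | SE (points) |
|---|---|---|---|---|---|---|
| 0% | 0 | 1.00% | 3.00% | 3.00 | 2.00 | 1.24 |
| 1% | 2.6 | 1.99% | 3.97% | 1.99 | 1.98 | 1.50 |
| 2% | 5.1 | 2.98% | 4.94% | 1.66 | 1.96 | 1.72 |
| 5% | 12.8 | 5.95% | 7.85% | 1.32 | 1.90 | 2.24 |
| 10% | 25.5 | 10.90% | 12.70% | 1.17 | 1.80 | 2.86 |

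The difference hardly moves. The ratio falls quickly, and the interval around the difference widens.

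**5. Chance imbalance (illustration).** Suppose p = 2%, about 10 of 510 participants. If each is equally likely to be in either arm, the probability of a 7:3 split or worse is 2 × (120 + 45 + 10 + 1)/1024 = 352/1024 ≈ 34%. If all ten exceeded at every draw, 7:3 would mean 49 against 21 exceedances with no treatment effect. That is a ceiling.

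**6. Lipids.** A value that passes 6.c or 6.d at screening can exceed the endpoint cut-off only if 1.5×ULN exceeds that cut-off. Cholesterol: 7.75/1.5 = 5.17 mmol/L. Triglycerides: 3.42/1.5 = 2.28 mmol/L. The documents state no laboratory ULN. At an assumed cholesterol ULN of 5.0 the entry cap is 7.50 (no gap); at 5.5 it is 8.25 (gap 0.50). At an assumed triglyceride ULN of 1.7 the cap is 2.55 (no gap); at 2.5 it is 3.75 (gap 0.33).

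**The case against.** The best defence is that little depends on these counts. They are exploratory, lie outside the test hierarchy of section 9.1.1, and are summarised by a risk difference, which step 4 shows to be nearly unaffected. Changes from baseline and shift tables are planned in the same section, liver-toxicity adverse events are tabulated as treatment-emergent, and possible severe liver injury is flagged by transaminases together with bilirubin or INR (Appendices 2 and 6), not by isolated bilirubin. Section 9 also leaves technical detail to the SAP, and no separate SAP text is in the supplied document, so a baseline rule there cannot be ruled out.

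Most of this stands and limits the weight of the point. It does not remove it. The laboratory categories defined in section 8.2.4 are low, normal and high, so a shift table on them shows a participant as high at both times but does not separate values above 1.5×ULN or 2.5×ULN.

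Three stronger readings are tempting, and the documents do not support them:

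- **That the definitions favour one treatment or will produce a false liver signal.** With 1:1 randomisation the expected inflation is equal in both arms, and other liver evidence would be read alongside.
- **That many participants are affected.** The exception in item 5a allows for the syndrome if it occurs; it predicts no number. For ALP the documents give no particular reason to expect entry above 2.5×ULN, and criteria 6.h, 12 and 13 may remove some such participants.
- **That the lipid endpoints share the fault to the same degree.** Criteria 6.c and 6.d cap screening values, so a gap at screening needs a ULN that the documents do not show. Otherwise it needs drift between screening and Day 1.

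**Conclusion.** The point holds for bilirubin and ALP: as written, an unchanged pre-existing elevation counts as an on-trial event, and nothing numeric in eligibility prevents it. The consequence is inflated absolute counts, a diluted risk ratio and more room for chance imbalance, without expected bias towards either arm.

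Its size cannot be estimated from the documents. The shares of 1% to 10%, the incidences of 1% and 3%, and persistence above the line at every draw are assumptions chosen to show direction and scale. The primary and key secondary analyses are untouched. This is a modest correction to exploratory safety definitions, worth making because it is cheap.

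**What to change.** In Table 3-2, section 9.3.11.3 and the SAP, define a bilirubin or ALP event as follows:

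- **Baseline at or below the cut-off:** a later value exceeds the cut-off.
- **Baseline already above the cut-off:** a later value exceeds a pre-specified multiple of that participant's baseline.

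The second part follows the ALT/AST approach and keeps genuine worsening in the count, which would be lost if these participants were simply removed. State that the multiple replaces the fixed cut-off. If baseline is above ULN, 3×baseline is always above 3×ULN, so the existing ALT/AST clause has an effect only when read as a replacement; the same sentence can make that explicit.

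Report the number above each cut-off at baseline by arm. For consistency only, apply the condition of a baseline value at or below the cut-off to triglycerides and cholesterol.

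No change to eligibility or stopping rules is implied. Baseline is already defined in section 9.3.1 and Day 1 chemistry is already drawn, so no visit, sample or sample-size change is needed. The cost is an edit to the protocol table and SAP before database lock, a little extra programming, and slightly fewer counted events.

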9.3.11.4 Participant's and Investigator's Assessment of Local Tolerability

Participant's and investigator's assessment of local tolerability for delgocitinib cream will be summarised by visit.

9.4 Interim Analyses

No interim analysis is planned during the trial.

9.5 Sample Size Determination

Approximately 510 participants will be randomly assigned to trial treatment in a 1:1 ratio, with 255 evaluable participants per treatment group. Approximately 660 participants will be screened to achieve this target.

With 510 participants randomised, the trial will provide 80% power to establish superiority of delgocitinib cream with regard to change from baseline to Week 12 in HECSI based on a 1-sided hypothesis test at a 2.5% significance level, assuming a difference in the mean change from baseline to Week 12 in HECSI of 7.5 (with a standard deviation of 30) between the 2 treatment arms (Ruzicka et al, 2008). Since there is limited published data on alitretinoin in terms of HECSI, anticipated treatment difference between delgocitinib and alitretinoin has been set using IGA scales as a surrogate endpoint (LP0133-1273 trial). Expected standard deviation is based on data observed in LP0133-1273 trial.

10 Supporting Documentation and Operational Considerations

10.1 Appendix 1: Regulatory, Ethical, and Trial Oversight Considerations

10.1.1 Regulatory and Ethical Considerations

This trial will be conducted in accordance with the protocol and with:

- Consensus ethical principles derived from international guidelines including the Declaration
 of Helsinki and Council for International Organizations of Medical Sciences (CIOMS)
 international ethical guidelines.
- Applicable ICH GCP guidelines.
- Applicable laws and regulations.

The protocol, protocol amendments, ICF, IB, and other relevant documents (e.g. advertisements) must be submitted to an IRB/IEC by the investigator and reviewed and approved by the IRB/IEC before the trial is initiated.

Any amendments to the protocol will require IEC/IRB approval before implementation of changes made to the trial design, except for changes necessary to eliminate an immediate hazard to trial participants.

Protocols and any substantial amendments to the protocol will require health authority approval prior to initiation except for changes necessary to eliminate an immediate hazard to trial participants.

The investigator will be responsible for the following:

- Providing written summaries of the status of the trial to the IRB/IEC annually or more frequently in accordance with the requirements, policies, and procedures established by the IRB/EC.
- Notifying the IRB/IEC of SAE or other significant safety findings as required by IRB/IEC procedures.
- Overall conduct of the trial at the site and adherence to requirements of 21 CFR, ICH GCP guidelines, the IRB/IEC, European regulation 536/2014 for clinical studies (if applicable), European Medical Device Regulation 2017/745 for clinical device research (if applicable), and all other applicable local regulations.

10.1.2 Financial Disclosure

Investigators and sub-investigators will provide the sponsor with sufficient, accurate financial information in accordance with local regulations to allow the sponsor to submit complete and accurate financial certification or disclosure statements to the appropriate regulatory authorities. Investigators are responsible for providing information on financial interests during the course of the trial and for 1 year after completion of the trial.

10.1.3 Informed Consent Process

The ICF(s) must be signed prior to performing any protocol related procedures, including but not limited to screening evaluations and initiation of wash-out for treatments listed as exclusion criteria.

The investigator or their representative will explain the nature of the trial, including the risks and benefits, to the participant and answer all questions regarding the trial.

Participants must be informed that their participation is voluntary. Participants will be required to sign a statement of informed consent that meets the requirements of 21 CFR 50, local regulations, ICH guidelines, privacy and data protection requirements, where applicable, and the IRB/IEC or trial site.

The medical record must include a statement that written informed consent was obtained before the participant was enrolled in the trial and the date the written consent was obtained. The authorised person obtaining the informed consent must also sign the ICF.

Participants must be re-consented to the most current version of the ICF(s) during their participation in the trial.

A copy of the ICF(s) must be provided to the participant.

Participants who are rescreened are required to sign a new ICF.

If a protocol amendment is required, the ICF may need to be revised to reflect the changes to the protocol. If the ICF is revised, it must be reviewed and approved by the appropriate IEC/IRB and signed by all participants subsequently enrolled in the trial as well as those currently enrolled in the trial.

10.1.4 Data Protection

Participants will be assigned a unique identifier by the sponsor. Any participant records or datasets that are transferred to the sponsor will contain the identifier only; participant names or any information which would make the participant identifiable will not be transferred.

The participant must be informed that their personal trial-related data will be used by the sponsor in accordance with local data protection law. The level of disclosure must also be explained to the participant who will be required to give consent for their data to be used as described in the informed consent.

The participant must be informed that their medical records may be examined by Clinical Quality Assurance auditors or other authorised personnel appointed by the sponsor, by appropriate IRB/IEC members, and by inspectors from regulatory authorities.

10.1.5 Dissemination of Clinical Trial Data

LEO Pharma is committed to be transparent with respect to its clinical trials.

Basic information of this clinical trial will be registered in the global data registry, www.ClinicalTrials.gov. before the first participant enters the trial. The trial may also become registered in other online data registries, according to applicable law and regulations.

Results of this clinical trial will be posted on leopharmatrials.com in accordance with our Position on Public Access to Clinical Trial Information within approximately 12 months of trial completion. Trial results may also become reported in www.ClinicalTrials.gov, www.clinicaltrialsregister.eu, and national data registries in accordance with applicable law and regulations after clinical trial completion or premature termination.

10.1.6 Data Quality Assurance

All participant data relating to the trial will be recorded on printed or electronic CRFs unless transmitted to the sponsor or designee electronically (e.g. laboratory data). The investigator is responsible for verifying that data entries are accurate and correct by physically or electronically signing the CRF.

Guidance on completion of CRFs will be provided in the CRF Completion Guidelines.

The investigator must permit trial-related monitoring, audits, IRB/IEC review, and Regulatory Agency inspections and provide direct access to source data documents.

Monitoring details describing strategies, including definition of trial critical data items and processes (e.g. risk-based initiatives in operations and quality such as risk management and mitigation strategies and analytical risk-based monitoring), methods, responsibilities and requirements, including handling of non-compliance issues and monitoring techniques (central, remote, or on-site monitoring) are provided in the Monitoring Plan.

The sponsor or designee is responsible for the data management of this trial including quality checking of the data.

The sponsor assumes accountability for actions delegated to other individuals (e.g. contract research organisations).

Records and documents, including signed ICF, pertaining to the conduct of this trial must be retained by the investigator for 25 years after trial completion unless otherwise required by local regulations or institutional policies. No records may be destroyed during the retention period without the written approval of the sponsor. No records may be transferred to another location or party without written notification to the sponsor.

All data generated by the site personnel will be captured electronically at each trial site using eCRFs. Data from external sources (such as laboratory data) will be imported into the database. Once the eCRF clinical data have been submitted to the central server at the independent data site, corrections to the data fields will be captured in an audit trail. The reason for change, the name of the person who performed the change, together with the time and date will be logged to provide an audit trail.

If additional corrections are needed, the responsible monitor or data manager will raise a query in the electronic data capture (EDC) application. The appropriate staff at the trial site will answer queries sent to the investigator. The name of the staff member responding to the query, and time and date stamp will be captured to provide an audit trail. Once all source data verification is complete and all queries are closed, the monitor will freeze the eCRF page.

The specific procedures to be used for data entry and query resolution using the EDC system/eCRF will be provided to trial sites in a training manual. In addition, site personnel will receive training on the EDC system/eCRF.

